4.1.2 Secondary endpoints

- Average pain score and duration of pain after administration (visual analogue scale) for each administration route at visits V1, V3, V5
- Reaction at site of injection (redness, swelling, induration, tenderness, ecchymosis, necrosis, nerve injury, infection) for IM and IV administration route at visits V1, V2, V3, V4, V5, V6,
- Vital signs (blood pressure, heart rate and respiratory rate) after administration for each administration route at visits V1, V2, V3, V4, V5, V6
- Solicited adverse events (fever, nausea, vomiting, diarrhoea, visual impairment, seizure)
- Number of participants with solicited local and systemic adverse events
- Number of participants reporting one or more adverse events and serious adverse events
- Correlation between serum and dry blood spot concentrations for each administration route at visits V1, V3, V5

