5.2 Inclusion visit (V1)

All **inclusion and exclusion criteria** have to be checked by physician, to ensure laboratory tests done at the screening visit are within normal values and for women, the pregnancy test is negative.

If a volunteer meets all inclusion and has no exclusion criteria and s/he consents to participate, the participant is considered **enrolled**. The investigator will randomize her/him to one of six groups (see Section 4.2.1).

Visit V1 (=1st drug administration):

- All women must have a **pregnancy test** (urine β hCG) done which must be negative to continue this visit.
- Participants medical history will be checked to ensure there are no changes since V0 visit.
- Baseline blood pressure, heart rate and respiratory rate will be recorded
- T₋₁: One blood sample will be taken for pharmacokinetics immediately prior to drug administration (0,5 mL venous blood taken in a dry tube without anti-coagulant)

- T₀: Drug Administration (PO, IV or IM) (as per randomization)
- **Pain assessment** using a Visual Analogue Scale (VAS) will be recorded immediately after drug administration and at 2 hourly intervals up to 8 hours. The VAS used will be the Numerical Pain Rating Scale where individuals rate their pain on a ten-point numerical scale. The scale is composed of 0 (no pain at all) to 9 (worst imaginable pain). The duration of any pain associated with IV or IM administration will be assessed once at 8 hours. Participants will be offered pain relief if needed in the form of simple analgesia (paracetamol).
The duration of any pain associated with IV or IM administration will be assessed once at 8 hours.
- Blood samples for **pharmacokinetics** (*0,5 mL of venous blood in dry tube without anti-coagulant*) will be taken at the following times after drug administration:
 - T₀+ 5min (only for IV route)
 - T₀+30min
 - T₀+1h
 - T₀+2h
 - T₀+3h
 - T₀+4h
 - T₀+5h
 - T₀+6h
 - T₀+8h (only for IM and PO routes)
- **Dry Blood Spot:** At one time-point (any time-point between T₀+ 5min and T₀+8h), a capillary blood sample will be taken at a finger with a lancet and a drop of blood will be placed on Mitra[®] device. An aliquot of 200µL of whole blood will be taken and aliquoted from the venous blood sample taken at the same time.

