5.3 Follow-up visits

Wash-out period between 2 drug doses is at least 48-hrs (but could be more). All the doses have to be completed within 3 months after the first dose.

Visit V2 (=visit V1 +24h):

- **Pain assessment** using a Visual Analog Scale will be recorded at T₀+24h (+/- 1 hour). The VAS used will be the Numerical Pain Rating Scale where individuals rate their pain on a ten-point numerical scale. The scale is composed of 0 (no pain at all) to 9 (worst imaginable pain). Participants will be offered pain relief if needed in the form of simple analgesia (paracetamol).
- **Vital signs** (blood pressure, heart rate and respiratory rate) recorded at T₀+24h (+/- 1 hour).
- Blood samples for **pharmacokinetics** (*0,5 mL of venous blood in dry tube without anti-coagulant*) will be taken at T₀+24h.
- **Reaction at site of injection:** Each injection site will be checked visually for local reaction and any other complications (including redness, swelling, induration, tenderness, ecchymosis, necrosis, nerve injury, infection) at T₀+24h (+/- 1 hour). Reaction will be measured in millimetre, and time of occurrence will be recorded.
- All the **adverse events** and **concomitant treatments** are collected

Visit V3 (=2nd drug administration (must be ≥ 48 hours from V1 T₀):

- All women must have a **pregnancy test** (urine βhCG) done which must be negative to continue this visit.
- Participants medical history will be checked to ensure there are no changes since V0 visit.
- Baseline blood pressure, heart rate and respiratory rate will be recorded

- T₋₁: One blood sample will be taken for pharmacokinetics immediately prior to drug administration (0,5 mL venous blood taken in a dry tube without anti-coagulant)
- T₀: Drug Administration (PO, IV or IM) (as per randomization)
- **Pain assessment** using a Visual Analogue Scale (VAS) will be recorded immediately after drug administration and at 2 hourly intervals up to 8 hours. The VAS used will be the Numerical Pain Rating Scale where individuals rate their pain on a ten-point numerical scale. The scale is composed of 0 (no pain at all) to 9 (worst imaginable pain). The duration of any pain associated with IV or IM administration will be assessed once at 8 hours. Participants will be offered pain relief if needed in the form of simple analgesia (paracetamol).
The duration of any pain associated with IV or IM administration will be assessed once at 8 hours.

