5.4 End of study visit

Due to the low toxicity of the molecule and its half-life ranging from 1 to 10 hours (depending on patient populations), healthy volunteers who participated in the study and received at least one administration of tranexamic acid will have a telephone follow-up after the end of the study. They will be contacted by **telephone 48 hours after the last administration** to check for any adverse events.

5.5 Expected length of participation, chronology and duration of the study.

Maximum period between screening and enrolment	7 days
Inclusion period	16 months
Duration of participation for each participant	Screen + 3x 2 days + 1 phone contact = over 3 months
Total study period	19 months

Table summarising the chronology of the study

Action	Visit V0 Screening	Visit V1 Inclusion	Visit V2 V1+24h	Visit V3	Visit V4 V3+24h	Visit V5	Visit V6 V5+24h	End of Study
Verification of Eligibility Criteria	X	X						
Signature of Informed Consent	X							
Demographic data	X							
Medical History	X							
Physical Examination, including weight and height	X							
Vital signs (including Blood pressure, heart rate, respiratory rate)	x	x	x	x	x	x	x	
Randomisation		x						
Drug Administration (PO, IM or IV)		X		X		X		
Pain (Visual Analogue Scale and duration of pain)		X	X	X	X	X	X	
Reaction at injection sites		X	X	X	X	X	X	
Laboratory Tests	X	X		X		X	X	
Haematology tests (full blood count)	x						x	
Renal function test (urea, creatinine, GFR)	x						x	
Coagulation tests (fibrinogen, D-dimers, prothrombin time and partial thromboplastin time)	x						x	
For women: pregnancy test (urine β hCG)	x	x		x		x	x	
Pharmacokinetic		X	X	X	X	X	X	
1 sample immediately prior to drug administration		x		x		x		
8 samples from T0+5min to T0+8h		x		x		x		
1 sample at T0+24h			x		x		x	
Dry Blood Spot: 1 capillary sample at any time-point between T0+5min and T0+8h and one 200 μ L whole blood aliquot of the venous sample taken at the same time		X		X		X		
Concomitant treatments	X	X	X	X	X	X	X	
Adverse Event		X	X	X	X	X	X	X
Telephone Follow-Up								X

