10 SAFETY ASSESSMENT - RISKS AND RESTRICTIONS ADDED BY THE STUDY

10.1 Safety endpoints

Safety Endpoints are:

- ✓ Number of participants with solicited local and systemic adverse events.
- ✓ Average pain score reported by participants during intramuscular administration (visual analogic scale)
- ✓ Duration of pain from intramuscular administration (hours)
- ✓ Local reaction at site of injection (redness, swelling, induration, tenderness, ecchymosis, necrosis, nerve injury, infection)
- ✓ Systemic events (fever, nausea, vomiting, seizure, diarrhoea, visual impairment)
- ✓ Vital signs (blood pressure, heart rate and respiratory rate) after administration

Number of participants reporting one or more adverse events and serious adverse events

10.2 Anticipated methods and timetable for measuring, collecting and analysing the safety endpoints

Safety Endpoints are recorded at each visit: for more details see sections 5.2 and 5.3.

- ✓ Pain is assessed by Visual Analog Scale (intensity from 0 to 9)
- ✓ Reaction at site of injection is assessed by visual inspection (measure in mm of the surface in case of reaction, and time of occurrence)

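### The pain endpoint is defined inconsistently across the protocol; if sections 5.2 and 5.3 are followed, duration is right-censored at 8 h, and no pre-dose score is taken

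*Protocol*

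**What the plan says.** Section 4.1.2 defines the secondary endpoint as "Average pain score and duration of pain after administration (visual analogue scale) for each administration route at visits V1, V3, V5". In the same list, the site-reaction and vital-sign endpoints run over V1 to V6.

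Sections 5.2 and 5.3 describe the collection. On each dosing day the pain score "will be recorded immediately after drug administration and at 2 hourly intervals up to 8 hours". For duration, the text reads "The duration of any pain associated with IV or IM administration will be assessed once at 8 hours"; oral dosing is not mentioned. The pre-dose record covers vital signs ("Baseline blood pressure, heart rate and respiratory rate will be recorded") and a PK sample, but not pain. At V2, V4 and V6 a pain score "using a Visual Analog Scale will be recorded at T₀+24h (+/- 1 hour") is taken, and the text has no duration question there.

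The schedule table in 5.5 has a single row, "Pain (Visual Analogue Scale and duration of pain"), marked at every visit from V1 to V6.

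Section 10.1 lists "Average pain score reported by participants during intramuscular administration (visual analogic scale") and, separately, IM pain duration in hours with no visit limit. Section 10.2 says safety endpoints are recorded at each visit and refers back to 5.2 and 5.3.

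On spacing, section 5.3 says: "Wash-out period between 2 drug doses is at least 48-hrs (but could be more").

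**The concern.** The stated scope of the trial includes assessing the safety of IM administration, which here means two separate 5 mL injections (section 7.1.1). Section 2.7 lists pain from the large-volume IM procedure as common. Pain is not among the specifically elicited adverse events, so the pain endpoint is the main systematic measure of it.

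If duration is asked once at 8 h and not again, the protocol can establish that pain lasted at least 8 h but not how long. A later analysis plan can choose how to handle that censoring. It cannot supply an answer that site staff, following 5.3, never asked for.

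A second, smaller matter is attribution. Without a score before dosing, any pain left from an earlier IM injection cannot be separated from pain caused by the next dose.

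**Working it through.** The protocol attaches no assumed value, precision or test to pain, so there is no planned figure to reproduce. The check is mainly a comparison of the text.

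**Sections side by side**

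| Question | 4.1.2 | 5.2 / 5.3 | Table in 5.5 | 10.1 / 10.2 |
|---|---|---|---|---|
| When is duration read? | V1, V3, V5 | once, at 8 h on dosing days | V1 to V6 | no visit limit; each visit |
| Does 24 h pain count? | no | score taken, no duration question | score and duration marked | each visit |
| Which routes? | all three | duration: IV and IM | not stated | IM only |
| After or during dosing? | after | immediately after, to 8 h, then 24 h | not stated | score: during; duration: from IM dosing |

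Two consequences follow. The oral duration required by 4.1.2 has no source in 5.2 or 5.3. And the 10.1 score, read literally, has no data behind it, because the first score comes immediately after dosing.

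**Censoring at 8 h under 5.2 and 5.3**

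Let T be the true duration. The single reading can establish at most min(T, 8 h). That holds for any distribution; only the size needs an assumption. As an illustration, take exponential T with median M (assumed values, none from the protocol). Then P(T > 8) = 2^(−8/M), the true mean is M/ln 2, and the mean capped at 8 h is (M/ln 2)(1 − 2^(−8/M)).

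| M | P(T > 8 h) | True mean | Mean if capped at 8 h |
|---|---|---|---|
| 4 h | 25% | 5.8 h | 4.3 h |
| 8 h | 50% | 11.5 h | 5.8 h |
| 24 h | 79% | 34.6 h | 7.1 h |

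The last column applies only if ongoing pain is entered as 8 h, which the protocol does not say. If the 24 h score is used, pain present at 8 h can be classed as ended between 8 and 24 h or as still present at 24 h.

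**Residual pain at the next dose**

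Of the six route orders, IM is followed by another dose in four: directly by IV in two and directly by oral in two. Fifteen volunteers in groups of 2 or 3 means three groups of each size. The four relevant groups therefore hold between 3×2 + 1×3 = 9 and 3×3 + 1×2 = 11 volunteers.

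At the minimum spacing, carry-over needs T > 48 h. Under the same assumption P(T > 48) = 2^(−48/M), and among about 10 exposed volunteers the chance of at least one case is 1 − (1 − p)^10:

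| M | P(T > 48 h) | At least one of 10 |
|---|---|---|
| 4 h | 0.02% | 0.2% |
| 8 h | 1.6% | 15% |
| 24 h | 25% | 94% |

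The range is too wide to say that carry-over will occur. It shows only that it cannot be excluded without a pre-dose score.

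**The case against.** The strongest reply is that the protocol does not settle on an 8 h limit. The schedule table places duration at the 24 h visits, and 10.1 and 10.2 do not confine it to dosing days. Staff working from the table would ask again at 24 h. This stands: the 8 h cut-off is one side of a contradiction, not a fixed rule.

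Nor is lasting pain lost altogether. The 24 h score is collected, section 12.1 tabulates individual and summary pain scores without a visit limit, site tenderness is checked at 24 h and at each later visit, and adverse events are followed until resolved. This also stands, in part. Persistence to 24 h is observable, but 4.1.2 leaves that score out of the endpoint, and a tenderness check gives no pain score to set against the next dose.

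On carry-over, 48 h is a minimum gap, and the duration question is tied to pain from IV or IM administration, so any contamination would mainly affect the score.

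A reader might infer that both weaknesses make IM look better than it is. The documents do not support that. They give no pain durations, do not say how ongoing pain is coded at 8 h, and apply the same reading to IV. A reader might also fault 12.1 for ignoring that each volunteer receives all three routes. Within-participant comparison of a descriptive endpoint can be left to the statistical analysis plan, so that is no fault here.

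**Conclusion.** The inconsistency is real and rests on the text alone: sections 4.1.2, 5.2/5.3, 5.5 and 10.1/10.2 disagree on when duration is read, whether 24 h pain counts, which routes are covered, and whether the score is taken during or after dosing. If 5.2 and 5.3 are followed, duration is right-censored at 8 h. How many volunteers that affects is unknown; the 25% to 79% above depends wholly on the assumed exponential shape and medians of 4 to 24 h.

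The missing pre-dose score is a lesser gap. It matters only if IM pain lasts at least 48 h, and only for the 9 to 11 of 15 volunteers who receive a dose after IM.

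The change is worth making because later analysis cannot recover the missing answers and the correction is cheap. It does not put the trial's main aim at risk: the endpoint is secondary and descriptive, and the primary PK endpoint is untouched.

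**What to change.** 1. Write one definition of the pain endpoint and use it in 4.1.2, 5.2/5.3, the table in 5.5 and 10.1: pain after administration, with the routes stated for score and for duration, over V1 to V6.
2. At V2, V4 and V6, ask again about duration where pain was ongoing at 8 h, and treat pain still ongoing then as censored at that visit.
3. Include the 24 h score in the endpoint.
4. Record one pain score immediately before dosing at V1, V3 and V5.

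The cost is one extra score at three visits that already take place, one extra question at the 24 h visits for those with ongoing pain, and matching wording in the protocol and case report form. No visit or blood sample is added.

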- **Reaction at site of injection:** Each injection site will be checked visually for local reaction and any other complications (including redness, swelling, induration, tenderness, ecchymosis, necrosis, nerve injury, infection) every fifteen minutes after administration for the first one hour then every two hours up to 8 hours after each injection and once at each subsequent visit. Reaction will be measured in millimetre, and time of occurrence will be recorded.

- Participants will have their **vital signs** (blood pressure, heart rate and respiratory rate) monitored and recorded at every fifteen minutes after administration for the first one hour then every two hours after drug administration.
- All **adverse events** and **concomitant treatments** will be recorded. The following adverse events will be elicited specifically (fever, nausea, vomiting, diarrhoea, visual impairment, seizure).

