- Blood samples for **pharmacokinetics** (*0,5 mL of venous blood in dry tube without anti-coagulant*) will be taken at the following times after drug administration:
 - T₀+ 5min (only for IV route)
 - T₀+30min
 - T₀+1h
 - T₀+2h
 - T₀+3h
 - T₀+4h
 - T₀+5h
 - T₀+6h
 - T₀+8h (only for IM and PO routes)
- **Dry Blood Spot:** At one time-point (any time-point between T₀+ 5min and T₀+8h), a capillary blood sample will be taken at a finger with a lancet and a drop of blood will be placed on Mitra[®] device. An aliquot of 200µL of whole blood will be taken and aliquoted from the venous blood sample taken at the same time.
- **Reaction at site of injection:** Each injection site will be checked visually for local reaction and any other complications (including redness, swelling, induration, tenderness, ecchymosis, necrosis, nerve injury, infection) every fifteen minutes after administration for the first one hour then every two hours up to 8 hours after each injection and once at each subsequent visit. Reaction will be measured in millimetre, and time of occurrence will be recorded.

- Participants will have their **vital signs** (blood pressure, heart rate and respiratory rate) monitored and recorded at every fifteen minutes after administration for the first one hour then every two hours after drug administration.
- All the **adverse events** and **concomitant treatments** will be recorded.

Visit V4 (=visit V3 +24h):

- **Pain assessment** using a Visual Analog Scale will be recorded at T₀+24h (+/- 1 hour). The VAS used will be the Numerical Pain Rating Scale where individuals rate their pain on a ten-point numerical scale. The scale is composed of 0 (no pain at all) to 9 (worst imaginable pain). Participants will be offered pain relief if needed in the form of simple analgesia (paracetamol).
- **Vital signs** (blood pressure, heart rate and respiratory rate) recorded at T₀+24h (+/- 1 hour).
- Blood samples for **pharmacokinetics** (*0,5 mL of venous blood in dry tube without anti-coagulant*) will be taken at T₀+24h.
- **Reaction at site of injection:** Each injection site will be checked visually for local reaction and any other complications (including redness, swelling, induration, tenderness, ecchymosis, necrosis, nerve injury, infection) at T₀+24h (+/- 1 hour). Reaction will be measured in millimetre, and time of occurrence will be recorded.
- All the **adverse events** and **concomitant treatments** are collected.

Visit V5 (=3rd drug administration):

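### The six solicited systemic events are written to be elicited only at V1 (15 of 45 administrations), which does not agree with section 10.2, and fever has no stated way of being ascertained

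*Protocol*

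**What the plan says.** Section 4.1.2 lists as secondary endpoints "Solicited adverse events (fever, nausea, vomiting, diarrhoea, visual impairment, seizure" and "Number of participants with solicited local and systemic adverse events". Neither entry names visits, although the entries for pain, site reactions, vital signs and dry blood spots do. Section 10.1 repeats the same six events as a safety endpoint: "Systemic events (fever, nausea, vomiting, seizure, diarrhoea, visual impairment".

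On collection, the protocol says:

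- **Section 5.2, V1 (first dose):** all adverse events are recorded, and in addition "The following adverse events will be elicited specifically (fever, nausea, vomiting, diarrhoea, visual impairment, seizure".
- **Section 5.3, V3 and V5 (second and third dose):** "All the adverse events and concomitant treatments will be recorded". There is no elicitation sentence.
- **Section 5.3, V2, V4 and V6 (24 hours after each dose):** "All the adverse events and concomitant treatments are collected". There is no elicitation sentence.
- **Section 5.4, call 48 hours after the last dose:** a general check for adverse events, with no list.
- **Section 5.5, schedule table:** one general adverse-event row covering V1 to V6 and the end of study, and no row for solicited events.
- **Section 10.2:** "Safety Endpoints are recorded at each visit: for more details see sections 5.2 and 5.3". It then describes how pain and site reactions are assessed, but gives no method for the systemic events.

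On fever, the schedule table itemises "Vital signs (including Blood pressure, heart rate, respiratory rate". Sections 4.1.2, 5.1, 5.2, 5.3 and 10.1 name the same three measurements.

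**The concern.** A solicited event is defined by being asked about. The V3 and V5 procedures otherwise repeat those of V1 almost item for item (pain, blood samples, dry blood spot, site checks, vital signs), but the elicitation sentence is missing. Staff who work from the visit text would put the six questions after the first dose and rely on general adverse-event enquiry after the second and third. One endpoint would then be gathered by two methods, and which method applies would depend on the period.

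Evaluating systemic safety by route is a secondary objective, and the summary gives the safety of intramuscular administration as part of the trial's scope. Mild nausea or a transient visual complaint is the kind of event that is reported more often when asked about. A question not put at the visit cannot be recovered later by an analysis plan, so this has to be settled in the protocol and the case report form.

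Fever adds a separate gap. It is a named component of the endpoint, but the protocol does not say whether it is measured or reported, or what counts as fever.

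**Working it through.** The protocol states no figure for this point. The check is a count of what the visit text covers, followed by what can and cannot be sized.

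**Inputs**
- 15 volunteers, 6 sequences of 2 or 3 volunteers (section 4.2.1).
- 3 doses each, one per route (section 2.6).
- Digestive events in more than 1/100 and fewer than 1/10 patients (section 2.7).

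**1. Administrations covered.** Planned administrations = 15 × 3 = 45. Those at V1 = 15. Covered share = 15/45 = 1/3. This is the count for completers. Replacing participants who miss a dose could add a few administrations.

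**2. Coverage by route.** A total of 15 from six groups of 2 or 3 requires three groups of 3 and three of 2 (3 × 3 + 3 × 2 = 15). Each route comes first in two of the six sequences, so the first doses by a route number 2 + 2 = 4, 2 + 3 = 5 or 3 + 3 = 6. Enumerating all allocations gives 5/5/5, or 4/5/6 in any order. Elicited doses per route are therefore 4 to 6 of 15.

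**3. Can the under-count be sized?** Let c be the share of events captured by general enquiry relative to elicitation. Assume full capture when elicited and the same event probability at each dose. Then:

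share missed = (2/3) × (1 − c)

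The protocol says nothing about c. Over its whole range, c = 1 gives 0 and c = 0 gives 2/3.

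Treating section 2.7's range as a per-dose rate (an assumption, since it is stated per patient), the expected events in 45 doses are 45 × 0.01 = 0.45 to 45 × 0.1 = 4.5. Missed events then run from 0 up to (2/3) × 0.45 = 0.30 at the low end, and from 0 up to (2/3) × 4.5 = 3.0 at the high end. These are bounds, not estimates. The endpoint also counts participants, not events.

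**4. Agreement between sections**

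| Section | V1 | V2, V4, V6 | V3, V5 | 48 h call |
|---|---|---|---|---|
| 5.2 to 5.4 | elicited | general | general | general |
| 10.2 | recorded | recorded | recorded | not stated explicitly |

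Section 10.2 sends the reader to 5.2 and 5.3 for detail, and the only elicitation detail there is under V1.

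**5. Fever.** No section reviewed includes a temperature reading or a fever definition.

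**The case against.** The strongest reply is section 10.2. The six events are safety endpoints, safety endpoints are recorded at every visit, and the missing sentence in 5.3 looks like a copying slip. This stands in part. It rules out a reading that a colleague might draw from 5.2 and 5.3 alone, namely that the endpoint is collected for only one third of administrations. It does not settle the matter, because recording an event is not the same as asking about it, and 10.2 defers to the sections where asking is specified once.

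Four further inferences are tempting, and the protocol does not support them:

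- **That doses 2 and 3 rely on passive reporting.** Participants are under repeated checks to 8 hours after every dose, are seen at 24 hours, and adverse events must be recorded at each visit. After the last dose the call is made in order to pick up adverse events. The contrast is between elicited and general enquiry.
- **That route comparisons are distorted.** Route order is randomised over all six sequences, so 4 to 6 of 15 elicited doses fall on each route. Any loss would be nearly equal across routes.
- **That the whole solicited endpoint is affected.** Local reactions are listed item by item and inspected at V1 to V6. Only the systemic list is in question.
- **That unequal follow-up after each dose is a defect.** The wash-out is at least 48 hours and the call is at 48 hours, so every dose has at least 48 hours of cover. The counting window can be left to the analysis plan.

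On fever, it is fair to say that participants can report it without a thermometer, and the word for inclusion in the schedule table does not strictly close the list. The lists in 4.1.2, 5.2 and 5.3 are closed, however, and nothing says that self-report is intended.

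**Conclusion.** The point holds as an inconsistency to be reconciled. The written instruction to elicit the six systemic events covers 15 of 45 planned administrations (4 to 6 of 15 per route), whereas section 10.2 implies the endpoint is recorded at every visit. If the visit text is followed, elicited and general reporting are mixed, and under-ascertainment after doses 2 and 3 is likely. That direction rests on the ordinary assumption that asking about an event finds at least as many as general enquiry.

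The size cannot be derived from the protocol. Any percentage shortfall would come entirely from an assumed capture rate. A capture of 30 to 70%, for example, would give (2/3) × 0.7 = 47% down to (2/3) × 0.3 = 20%, but nothing in the protocol supports those rates.

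Fever lacks a stated method of ascertainment and a definition.

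This is a should-fix. The endpoints are secondary and are to be summarised and tabulated. The primary endpoint is serum concentration, and the sample size rests on pharmacokinetic precision, so neither is touched.

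**What to change.** - In section 5.3, repeat the V1 elicitation sentence at V3 and V5, and at V2, V4 and V6. Add it to the 48-hour call in section 5.4. Section 5.3 then agrees with 10.2, and elicited dosing days rise from 15 of 45 to 45 of 45, or 15 of 15 per route.
- In section 4.1.2, name these visits for the solicited-event endpoint, as is done for pain, site reactions and vital signs.
- For fever, either add a temperature reading to the existing vital-sign checks together with a definition of fever, or state that fever is participant-reported.
- Carry the same list into the case report form pages for each visit and the call.

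The cost is protocol and case report form wording and, if that option is chosen, a temperature reading at checks already scheduled. No visit or blood sample is added, and the sample size does not change.
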